3.3 Safety considerations

For further information on the safety of camostat and specific safety considerations refer to the current version of the 'Camostat Investigator's Brochure'.

3.3.1 Adverse events

Camostat has been in clinical use for over 30 years in Japan and Korea and has a known, acceptable safety profile. Adverse reactions reported during the safety surveillance of camostat for its licensed indications include shock or anaphylactoid symptoms, thrombocytopenia, changes in liver enzymes, gastrointestinal disorders, rash and hyperkalaemia, all with low reported incidences (<1% patients).

3.3.2 Patient population

The majority of clinical studies supporting the original registration of FOIPAN® in Japan were conducted in a Japanese/Asian population.

Two Phase I PK studies have been performed in Caucasians, one by Forrest, 1989 and one by Midgley, 1994. Camostat is rapidly metabolised in vivo by a carboxyesterase to its active metabolite GBPA and the inactive by product 4-guanidinobenzoic acid (GBA) (Midgley, 1994). The active metabolite GBPA is further metabolized by arylesterase, glucuronidated and excreted in the urine (Midgley, 1994). Genetic variations due to ethnicity have not been reported for any of these enzymes involved in the metabolism

of camostat. From the available data, it is concluded that the PK/PD differences between the Asian and Caucasian populations are predicted to be minimal and that the known safety of camostat in Asians and Caucasians is expected to be similar (Forrest, 1989) (Midgley, 1994).

3.3.3 Risk and benefit assessment

For the overall risk and benefit assessment for the investigation of camostat in protocol CRUKD/20/002, refer to Section 5.8 in the current version of the 'Camostat Investigator's Brochure'.

4 OBJECTIVES AND ENDPOINTS

Primary Objective and Endpoint	
Objective	Endpoint
To further assess the safety and toxicity profile of camostat, to support integration into a Phase III trial.	Causality and severity of each adverse event (AE) to camostat.
Secondary Objectives and Endpoints	
Objective	Endpoint
To confirm that the PK profile aligns with the established PK profile for the active metabolite of camostat, 4-(4-guanidinobenzoyloxy) phenyl acetic acid (GBPA).	Confirm PK parameters of GBPA as assessed by population estimates from population PK analysis (popPK).
To assess the ability of camostat to reduce the requirement for COVID-19 related hospital admission in community patients with SARS-CoV-2 infection.	Rate of COVID-19 related hospital admission in community patients with SARS-CoV-2 infection.
To evaluate the requirement for supplementary oxygen (non-invasive or mechanical invasive) in patients who have received camostat as treatment for SARS-CoV-2 infection.	Supplementary oxygen-free days at 28 days (from randomisation).
To evaluate the requirement for ventilation in patients who have received camostat as treatment for SARS-CoV-2 infection.	Ventilator-free days at 28 days (from randomisation).
To evaluate efficacy of camostat by effect on COVID-19 related clinical improvement.	
Time Frame: Days 1-28
 
Time to worst point on the scale or deterioration of two points or more (from randomisation) on a 9-point category ordinal scale.
 
9-point category ordinal scale:
 
 0. Uninfected, no clinical or virological evidence of infection 1. Ambulatory, no limitation of activities 2. Ambulatory, limitation of activities 3. Hospitalised – mild disease, no oxygen therapy 4. Hospitalised – mild disease, oxygen by mask or nasal prongs 5. Hospitalised – severe disease, non-invasive ventilation or high-flow oxygen 6. Hospitalised – severe disease, intubation and mechanical ventilation 7. Hospitalised – severe disease, ventilation and additional organ support – vasopressors, renal replacement therapy (RRT), extracorporeal membrane oxygenation (ECMO) 8. Death

Research Objectives and Endpoints	
Objective	Endpoint
[REDACTED]	[REDACTED] [REDACTED] [REDACTED]
[REDACTED]	[REDACTED] [REDACTED] [REDACTED] [REDACTED] [REDACTED]
[REDACTED]	[REDACTED] [REDACTED]

5 TRIAL DESIGN

5.1 Summary of trial design

A randomised, multicentre, prospective, open label clinical trial.

The trial aims to recruit up to 100 patients.

The Trial Management Group (TMG) described in Section 5.2.1, will perform ongoing review of the emerging data to inform adaptive decision making during the trial. Please see Section 5.2.1. for further details.

During the trial, patient enrichment strategies may be implemented e.g. adapting the inclusion criteria to include emerging co-morbidities, neutrophil/lymphocyte ratio, other blood biomarkers, age, in order to support trial endpoints and feasibility. All clinical data will be reviewed on a regular basis by the Sponsor and TMG to inform this adaptive design, collaborating with the Trial Steering Committee (TSC) as per Section 5.2.2.

If review of the data (during any part of the trial) results in proposed substantial amendments, these will be submitted to the Medicines and Healthcare products Regulatory Agency (MHRA) and Research Ethics Committee (REC) for an opinion.

Patients may be identified in/through various settings e.g. GP practices, primary care COVID hubs, community-based testing centre, drive through testing facilities, advertisement, secondary care or equivalent clinical settings. Further detail on how patients will be recruited is provided in Section 9.1. It is likely that testing availability and strategy will change in the UK and the trial will respond by engaging with testing sites as applicable, to support recruitment. Before any new sites are opened for this trial, risk assessments will be performed to ensure that the protocol and procedures can be performed safely for both patients and site staff.

If a patient consents to the trial and fulfils eligibility criteria, they will be randomised to either the treatment arm or the control arm. Patients in the treatment arm will be asked to take camostat for 14 consecutive days and patients in the control arm will be asked to continue with best supportive care.

A clinical research team member will call the patient daily during this period. On Days 7 and 14, patients will be visited at home by the clinical research team, for blood draws and COVID-19 swab (or equivalent) testing. Home visits may be replaced by patient site visits (e.g. to a 'red hub') but only in accordance with government and clinical advice. If the Sponsor and site decide that sampling is not required, this will be communicated to the patient. The video (phone) calls on Days 7 and 14 will still go ahead as planned regardless of sampling. Patients will also be called weekly (Days 21 and 28) before the follow up period ends.

Patients who are in hospital for non COVID-19 related reasons may be recruited if they tested positive while in hospital. In this situation daily phone calls may be substituted by face to face visits, if feasible, by the hospital team until the patient is discharged. At that point the patient will be managed as described above. Further detail on how patients will be recruited and managed in this situation is provided in Section 9.

Adverse events (AEs) or hospital admissions related to camostat or COVID-19 will be followed up as per Section 12.0.

During the trial period (Days 1-28), patients who are hospitalised will also be followed up, up to 28 days post discharge.

5.2 Safety oversight and committees

5.2.1 Trial Management Group

The TMG is responsible for the day to day running of the trial including but not limited to, the Sponsor, Chief Investigator (CI), Trial Statistician, Principal Investigators (PIs) and Co-Investigators who will have oversight of all clinical and safety data throughout both phases of the trial. A core study team will oversee management of the trial and make decisions at the operational level.

Early assessment of recruitment and trial feasibility will be critical therefore the TMG will provide ongoing review of emerging clinical and feasibility data during the trial and propose modification where required for regulatory/ethical approval as appropriate. The TSC will be asked for an opinion as appropriate when these modifications are proposed by the TMG.

5.2.2 Trial Steering Committee

A TSC will be convened to review safety and pharmacokinetic data from the trial on an ongoing basis. The TSC will include the CI, Sponsor representatives including the Medical Advisor, at least two independent experts with expertise in COVID infection and/or other relevant specialities, trial statistician and one member of the Sponsor's Protocol and Safety Review Board⁶ (PSRB).

The TSC will provide expert advice in the event of any concerns around toxicity and will have the authority to suspend or terminate the trial and/or make recommendations to the Sponsor to modify the trial design.

Meetings of the TSC will be convened by the Clinical Study Manager (CSM) for the trial to review data generated at time points where key decisions are required. Additional ad hoc meetings may be convened should unforeseen events occur, and independent expert advice would be beneficial.

The responsibility for calling and organising TSC meetings lies with the CSM for the trial in association with the Chair of the TSC. Meetings will take place at least every six months if a review has not already taken place. The TSC, CI or Sponsor can request additional meetings at any time.

A TSC Charter will be made available to support the trial. The charter will include reference to the Statistical Analysis Plan (SAP) and how results from any analysis will be communicated to the TSC to inform decision making.

5.2.3 Safety oversight

Safety evaluations by the TMG will be conducted at regular intervals throughout patient recruitment. Data reviewed includes all clinical data, safety data listings and trial feasibility. Any concerns relating to safety can be escalated to the TSC for an opinion and recommendation.

5.3 Intervention

5.3.1 Randomisation

Patients will be randomised by the site staff using an interactive web response system (IWRS). Confirmation of the patient randomisation will be sent to the Investigator, site clinical trial team and Sponsor following enrolment and randomisation of the patient. The patient will be notified of their allocated group by the clinical research team.

Randomisation will be to one of two arms and a randomisation ratio of 1:1 will be applied:

- **Treatment arm:** patient to receive treatment with camostat 200 mg qds for 14 days.
- **Control arm:** patients will receive best supportive care.

⁶ The PSRB acts as an independent body across the portfolio of studies at the CR UK Centre for Drug Development (CDD). The PSRB charter mandates that the members are independent from CR UK, CDD and can act as an independent body.

All patients randomised will receive a trial pack to include [REDACTED]

[REDACTED] instructions for use as well as a diary card to record these readings and, if randomised to camostat, to document their compliance with dosing. If patients wish to do so, they can use the Medidata patient application ('app') in addition to the diary card. The trial pack will include an app instruction and consent document. The research team or courier will deliver the appropriate trial pack.

For patients recruited while in hospital, all assessments will be performed and camostat will be given by the hospital staff (if the patient is randomised to camostat). Patients will receive a trial pack to include [REDACTED] instructions for use only on discharge. If patients wish to do so, they can use the Medidata patient application ('app') in addition to the diary card and app instructions and consent form can be provided.

Patients randomised to the treatment arm will also be offered best supportive care in managing the disease.

5.3.2 Dose modification

The planned dose for all patients who are randomised to the treatment arm is 800 mg per day (200 mg *qds*) for 14 days. Dose modifications may occur such as reducing the daily dose. Dose reductions for individual patients may be considered based on emerging clinical data and if agreed with the Sponsor, CI and PIs. These dose reductions could take the form of reduction of times that camostat is administered e.g. *qds* to *tds* or to a reduction at each of the daily administrations e.g. 200 mg *qds*, down to 100 mg *qds*.

The patient will be contacted daily during the treatment period by the clinical research team for assessment of any AEs and difficulties the patient may be experiencing with the administration schedule.

Escalation of patient management is further discussed in Section 8.5.

5.3.3 Dose interruptions/ Withdrawal criteria

- If a clinically significant abnormality is identified, camostat will be interrupted and blood samples will be taken for analysis.
- If abnormal results are identified, the patient will be referred to the GP for further assessment where local protocols will be followed.
- If required, patient hospital attendance with a suspected adverse event will trigger SAE reporting and the Investigator and Sponsor will make a causality assessment.
- Possible, Probably and Highly Probable causality assessment to camostat will result in treatment withdrawal.
- If the patient recovers symptomatically and biochemical analysis returns to the normal range, re-starting camostat can be considered by the Investigator and Sponsor to include an assessment whether the patient is likely to be past the initial stage of infection. For patients where it is deemed appropriate to re-start the patient, a maximum of 48 hrs treatment interruption will be allowable.

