6.2 Exclusion Criteria

The patient may not enter the trial if ANY of the following apply:

1. Significant electrolyte disturbance (e.g. hyperkalaemia, potassium > site specific upper limit of normal).
2. Alanine aminotransferase (ALT) and/or aspartate aminotransferase (AST) and/or alkaline phosphatase (ALP) $\geq 2.5 \times$ ULN.
3. Any condition that, in the Investigator's opinion, would not make the patient a good candidate for the clinical trial or would prevent adequate compliance with trial therapy e.g. mild cognitive impairment (unable to follow instructions for self-assessment readings as assessed by the Investigator).
4. Patients on long term supplementary oxygen requirement (patients for whom hospital admission would not be considered e.g. care plan in the community is in place, are not excluded).
5. Known hypersensitivity to camostat.
6. Platelet count $<100 \times 10^9/L$.
7. Co-enrolment with a Clinical Trial of an Investigational Medicinal Product (CTIMP) will not be permitted. Co-enrolment with a clinical investigation of a Medical Device or a non-interventional clinical study will be considered on a study-by-study basis and in discussion with the relevant Chief Investigators and Sponsors and industrial collaborators.
8. Co-enrolment involving non-interventional research (including questionnaire or tissue only studies) will be allowed provided this is not expected to affect the outcomes of both studies or place undue burden upon participants and their families.
9. Female patients who are able to become pregnant⁷ (or are already pregnant or lactating). However, those patients who are of child bearing potential and have a negative serum or urine pregnancy test before enrolment and agree to use two forms of contraception (one effective form plus a barrier method [oral, injected or implanted hormonal contraception

⁷ A woman is considered of childbearing potential i.e. fertile, following menarche and until becoming post-menopausal unless permanently sterile. Permanent sterilisation methods include hysterectomy, bilateral salpingectomy and bilateral oophorectomy. Post-menopausal state is defined as no menses for 12 months without an alternative medical cause. A high follicle stimulating hormone (FSH) level in the postmenopausal range may be used to confirm a post-menopausal state in women not using hormonal contraception or hormonal replacement therapy. However, in the absence of 12 months of amenorrhea, a single FSH measurement is insufficient.

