12.3 Procedures for Recording Adverse Events

All AEs will be recorded in the eCRF.

The following information will be recorded: patient ID including the patient trial number, age and gender; verbatim term for the AE description, date of onset and end date as well as outcome, severity of the event, assessment of relatedness to trial medication, other suspect drug or device and action taken. Follow-up information should be provided as necessary. AEs should be recorded on the CRF from the date of written/verbal informed consent (whichever is the earlier) being given until they have completed the 28 days from Day 1 follow up period.

AEs considered related to the trial medication or COVID-19, as judged by a medically qualified investigator or the sponsor will be followed until resolution or the event is considered stable. All related AEs that result in a patient's withdrawal from the trial or are present at the end of the trial, should be followed up until a satisfactory resolution occurs.

It will be left to the investigator's clinical judgment whether or not an AE is of sufficient severity to require the patient's removal from treatment. Although the Sponsor will hold the final decision if there is a disagreement in the management of the patient's treatment. A patient may also voluntarily withdraw from treatment due to what he or she perceives as an intolerable AE. If either of these occurs, the patient must undergo an end of study assessment and be given appropriate care under medical supervision until symptoms of the AEs cease or the condition becomes stable.

The severity of events will be assessed on the following scale: 1 = mild, 2 = moderate, 3 = severe and as judged by a medically qualified investigator.

For hospitalised patients who are admitted (for any reason other than COVID-19) and subsequently test positive for COVID-19, medical occurrences or symptoms of deterioration that are expected as a consequence of the participant's admission hospital should be recorded in the patient's medical notes and only be reported as AEs in the eCRF if medically judged to have unexpectedly worsened during the study. AEs considered related to the trial medication or COVID-19, as judged by a medically qualified investigator or the sponsor will be reported in the eCRF.

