6.4 Protocol deviations

A protocol deviation is defined as any departure from what is described in the protocol of a clinical trial approved by an Independent Ethics Committee and Competent Authorities. Therefore, it applies to deviations related to patient inclusion and clinical procedures (e.g. assessments to be conducted or parameters to be determined), and also to other procedures described in the protocol that concern the Good Clinical Practice (GCP) guidelines or ethical issues (e.g. issues related to obtaining the patients' Informed Consent, data reporting, the responsibilities of the Investigator, etc.).

Protocol deviations are captured throughout the trial open phase on the Sponsor's central tracker and can be filtered by study and by deviation category or on the study specific PK/PD deviations tracker. Standard deviation categories have been defined by the Sponsor and are further defined by those which are deemed reportable (important deviations) in the Clinical Study Report (CSR). Those deviations which have been coded as CSR reportable will be summarised for all patients, according to the categories allocated at identification. Deviations are reviewed manually as per Sponsor SOPs.

A summary table with the number of patients with deviations will be presented per criterion. Deviations with no effects on the risk/benefit ratio of the clinical trial (such as minimal delays in assessments or visits) will be distinguished from those that might have an effect on this risk/benefit ratio.

The following are pre-defined protocol deviations with a direct bearing on the primary outcome and therefore will be reported in the CSR. A summary including but not necessarily restricted to the following categories will be presented:

- Ineligible patients as per protocol.
- Patient not withdrawn as per protocol.
- Excluded concomitant medication.
- Incorrect IMP dose or schedule

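### Protocol 5.3.3 makes camostat withdrawal follow automatically from a drug-related rating, 12.3 leaves it to judgement of severity, and neither takes precedence, so failure to withdraw cannot be coded consistently as a deviation

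*Protocol*

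**What the plan says.** Protocol section 5.3.3 lists its criteria as bullets. One says that hospital attendance with a suspected adverse event triggers SAE reporting and a causality assessment by Investigator and Sponsor. The next reads: "Possible, Probably and Highly Probable causality assessment to camostat will result in treatment withdrawal". It states no severity condition. The last bullet says that once the patient has recovered symptomatically and "biochemical analysis returns to the normal range, re-starting camostat can be considered", and that for those who restart "a maximum of 48 hrs treatment interruption will be allowable".

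Protocol section 12.3, on adverse events in general, says it is "left to the investigator's clinical judgment whether or not an AE is of sufficient severity to require the patient's removal from treatment". The Sponsor has the final say where there is disagreement.

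Protocol section 5.3.2 adds: "Dose reductions for individual patients may be considered based on emerging clinical data", subject to agreement by the Sponsor, CI and PIs. Section 12.2 asks assessors, when rating causality, to weigh what happened after the drug was stopped or its dose lowered, and after it was restarted. Section 6.2 excludes patients with ALT, AST or ALP at or above 2.5 x ULN, and so admits those between the upper limit of normal and that value.

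SAP section 6.4 includes "Patient not withdrawn as per protocol" among the pre-defined deviations that it links directly to the primary outcome and will report in the CSR.

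**The concern.** The same event can be handled in two ways, each supported by the protocol. If an investigator rates an event as possibly related but judges it not severe enough to stop the drug, continuing is a failure to withdraw under 5.3.3 and compliant under 12.3. Sites may then differ in practice, and so may the people who code deviations.

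Three outputs are affected: the count of reportable failures to withdraw, the adverse-event withdrawals in SAP Tables 6 and 7, and exposure to camostat. A patient withdrawn before five days of dosing also leaves the efficacy population (Protocol 13.1; SAP 5.1).

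There is also a link to the primary endpoint, which is the causality and severity of each adverse event (Protocol section 4). The cut-point that defines a drug-related event (Protocol 12.2; SAP 6.7) is the one that triggers withdrawal in 5.3.3. In an open-label trial, attaching an automatic consequence to that rating may influence borderline calls.

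**Working it through.** The plan gives no figure on this point, so the check is mainly a comparison of the texts.

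**Scope of the 5.3.3 bullet.** Broad reading: it covers every adverse event, because the sentence carries no limit, the section heading names withdrawal criteria generally, and sections 8.3.2 and 8.5 send sites to 5.3.3 for those criteria. Narrow reading: it refers back to the causality assessment in the preceding bullet, made at hospital attendance.

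**The two rules side by side**

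| Event | 5.3.3, broad | 5.3.3, narrow | 12.3 |
|---|---|---|---|
| Mild, managed at home, rated possible | withdraw | not covered | judgement of severity |
| Hospital attendance/SAE, rated possible or higher | withdraw | withdraw | judgement of severity |
| Rated unlikely or not related | not covered | not covered | judgement of severity |

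The broad reading gives a conflict in rows 1 and 2. The narrow reading still leaves one in row 2, because 12.3 applies to all adverse events. No text ranks the sections.

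**Restart and dose reduction.** 5.3.3 does not say whether restart is open after an event rated drug-related. 5.3.2 ties reduction to emerging clinical data and names no adverse event. Section 12.2 expects evidence from a lowered dose and from re-challenge, which suggests that some patients with suspected reactions continue or resume. These are ambiguities about who is covered.

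**Restart laboratory condition.** A patient may enter with, say, ALT above 1 x ULN and below 2.5 x ULN. 5.3.3 refers to a return to normal, with interruption capped at 48 hours. Such a patient was not in the normal range at entry, and some may be unable to reach it in that time. The text does not say how the condition applies to them. Potassium does not raise the same entry problem: section 6.2 gives a value above the site's upper limit as an example of an excluded disturbance.

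**Illustration of size (assumed rates, broad reading).** Inputs: 50 camostat patients (SAP section 4); share r with at least one event rated possible or higher, assumed 5% to 40%; share s of those whom a severity judgement would stop, assumed 25%. Section 3.3.1 reports incidences below 1% at licensed use for the reactions it lists, which does not give an overall rate here.

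- Automatic rule: 50 x r = 50 x 0.05 = 2.5, to 50 x 0.40 = 20 patients.
- Severity judgement: 50 x r x s = 2.5 x 0.25 = 0.6, to 20 x 0.25 = 5 patients.
- Lost to the efficacy population, if onset is uniform over 14 days and 4 of 14 days precede completion of five days' dosing: 2.5 x 4/14 = 0.7 to 20 x 4/14 = 5.7 under the automatic rule, against 0.2 to 1.4 under judgement.

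On the narrow reading the numbers would be smaller, by an amount the documents do not allow one to estimate.

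**The case against.** The strongest reply is that 5.3.3 describes a pathway: abnormality, interruption and blood tests, GP referral, hospital attendance, joint causality assessment, then withdrawal. Read so, a mild related event at home need not lead to withdrawal. This is a fair reading and removes row 1 of the table. It leaves row 2, and the protocol does not say that it is the intended reading. A site could satisfy both sections by always withdrawing, but the discretion in 12.3 would then have no effect for these events.

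A reader might infer that four rules contradict one another. The documents do not support that. Dose reduction has a different stated trigger, and restart can be read as covering only interruptions for unrelated events, since 5.3.3 separates interruption from withdrawal.

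A reader might also infer that a patient with raised enzymes at entry can never meet the restart condition. That is too strong: enzymes can normalise, and the condition may refer to the parameter that prompted the interruption.

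Finally, a reader might infer that the causality endpoint is biased downward. Sponsor review limits this. Section 12.1.4 has the Sponsor's drug development centre assess causality for all adverse events, and under 12.1.2 an event counts as a reaction if either the reporter or the Sponsor suspects it. The primary outcome is also summarised as number and severity of events (Protocol 13.1) and compared between arms (SAP section 12), which does not rest on causality. An influence on borderline ratings remains possible but is not shown.

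**Conclusion.** The conflict between 5.3.3 and 12.3 stands on the text and needs no numerical assumption. It affects drug-related hospital-attendance events on the narrow reading and all drug-related events on the broad one. While it stands, the SAP 6.4 category has no single rule to be coded against for withdrawal after an adverse event. That sites will act differently is an inference. The Sponsor's role in disagreements reduces that risk without removing it.

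Restart, dose reduction and the laboratory condition are related ambiguities of lesser weight. The patient counts are illustrations that depend on assumed rates and the broad reading; they do not measure the effect. The point should be dealt with because it bears on patient safety and on the reporting of withdrawals. It does not make the safety comparison uninterpretable.

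**What to change.** The sponsor should reconcile Protocol sections 5.3.2, 5.3.3, 6.2, 12.2 and 12.3 into one rule of its own choosing. The text should state:

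- which events the causality bullet covers, and whether 5.3.3 or 12.3 prevails;
- whether dose reduction and restart are open after a drug-related event, consistently with the guidance in 12.2;
- how the restart laboratory condition and the 48-hour limit apply to patients admitted under 6.2 with enzymes above normal.

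SAP section 6.4 should then define its failure-to-withdraw deviation against that rule. No particular clinical rule is proposed here. Nor is a lock on causality ratings: section 12.2 relies on evidence seen after the drug is stopped or restarted, and the action taken is already recorded separately from relatedness (Protocol 12.3; SAP 6.7).

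The cost is protocol amendment wording and one line in the SAP, with no added procedures or data collection.
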